4.1.1.1 Intra-patient Dose Escalation

Intra-patient dose escalation to a higher dose level may be permitted by the sponsor, provided that the current dose level the patient is on has been cleared of DLT (safe and tolerable), and the higher dose level cohort being considered has also been cleared of DLT (safe and tolerable) prior to the start of that intra-patient dose escalation. There must be at least 28 days in-between the last dose of the current/lower dose level and the start of next/higher dose level and the patient must have tolerated the current/lower dose level.

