2.3 Clinical Experience of HMPL-689

See the investigator's brochure (IB) for up-to-date clinical experience for HMPL-689.

Study CCI (Completed)

This was a phase 1, randomized, double-blind, placebo-controlled, first-in-human, single dose escalation study to investigate the safety, tolerability and PK of HMPL-689 in Australia (completed). The study enrolled 48 healthy volunteers who were randomized into HMPL-689 group or placebo group at a 3:1 ratio. Subjects received oral single doses of HMPL-689 or placebo in sequence at dose levels of 1, 2.5, 5.0, 10, 20, and 30 mg under fed condition.

Of 36 subjects in the HMPL-689 treatment group, 15 subjects (41.67%) experienced a total of 19 adverse events (AEs). Adverse events reported in at least one subject included upper respiratory tract infection (13.9%), headache (8.3%), dyspepsia (5.6%), oligospermia (5.6%), flatulence (2.8%), back pain (2.8%), musculoskeletal pain (2.8%), eczema (2.8%), skin burning sensation (2.8%), and eye irritation (2.8%). Adverse events that were assessed by the investigator as related to HMPL-689 were upper respiratory tract infection (8.3%), headache (5.6%), dyspepsia (5.6%), flatulence (2.8%), and back pain (2.8%). Alanine transaminase increase was noticed in 5.56% of subjects in the HMPL-689 group and 8.33% of subjects in the placebo group. Aspartate transaminase increase was noticed in 19.44% of subjects in the HMPL-689 group and 25% of

subjects in the placebo group; all of the ALT/AST increases were of Grade 1. No Grade ≥ 3 AE was reported. No dose limiting toxicity (DLT) was noted.

The single dose PK of HMPL-689 was evaluated in 36 healthy volunteers in the HMPL-689 treatment group under fed condition. HMPL-689 was absorbed after oral administration with a median T_{max} of 1.5 to 3 hours. The HMPL-689 exposures, as measured by C_{max} and AUC, increased with dose increase from 1 to 30 mg after single dosing. The geometric means of apparent volume of distribution (V_z/F) and apparent oral clearance (CL/F) were approximately 209-268 L and 18.2-23.0 L/h, respectively, across all dose levels. The geometric mean $t_{1/2}$ values were similar across dose levels, with values ranging from 7.06 to 9.37 hours.

Study CCI [REDACTED] (Completed)

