4.1.1.3 Dose Limiting Toxicity Assessment Window

For all patients in Stage 1, DLTs will be assessed during a DLT assessment window of 28 days (i.e., from Cycle 1, Day 1 [the day of first administration of treatment] through Cycle 1, Day 28).

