4.1.1.4 Definition of a DLT-Evaluable Patient

For decisions on dose escalation, each dose cohort shall present protocol-required number of DLT-evaluable patients. Any patient is DLT evaluable if he/she meets the following criteria:

A patient is DLT evaluable if he/she:

- has received at least 75% of the assigned dose of study treatment during the DLT assessment window (i.e., Days 1-28);
- or
- has not completed the DLT assessment period due to a DLT.

Patients who are not DLT evaluable in a dose cohort will be replaced to guarantee the protocol-required number of DLT-evaluable patients for each dose cohort.

4.1.1.5 Dosing Beyond Cycle 1

Patients who complete DLT assessment window and are deemed by the investigator to be benefiting from HMPL-689 treatment may continue with HMPL-689 treatment until disease progression, death, intolerable toxicity, at investigator's discretion that the patient can no longer benefit from the study treatment, withdrawal of consent, or the end of study, whichever occurs first. Conversely, if, in the opinion of the attending principal investigator, the patient may receive clinical benefit from a higher dose, then, at the request of the principal investigator and with the approval of the sponsor, the patient may be able to participate in intra-patient dose escalation (Section 4.1.1.1).

During the study treatment period, including the DLT assessment window, patients will not be allowed to make up missed doses.

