4.2 Rationale for the Starting Dose and Dosing Schedule

The starting dose of this multiple doses study in human is determined according to the final result of the single dose study in healthy volunteers, the preliminary result of the multiple doses study in patients with lymphoma, as well as the result of the non-clinical toxicity studies.

In the HMPL-689 single dose escalation first-in-human study (CCI [REDACTED]), single dose of HMPL-689 30 mg was well tolerated with no DLT or SAE noted. The exposures of HMPL-689 measured by geometric mean AUC_{0-24h} values in human at dose levels of 1, 2.5, 5, 10, 20 and 30 mg were 39.9, 98.2, 195, 446, 877, and 1280 h•ng/mL, respectively. The geometric mean $t_{1/2}$ of HMPL-689 was around 7-9 hours.

In the multiple dose escalation study (CCI [REDACTED]), 2 DLTs were observed at 5 mg BID, and no DLT was observed at 2.5 mg BID or 5 mg QD. Re-challenging of 5 mg BID and evaluating of 10 mg QD were ongoing at the data cut-off date of 30 April 2018. The PK profile in Chinese patients with lymphoma on Day 1 was similar to that in male healthy volunteers in Australia with regard to $t_{1/2}$ and exposures (C_{max} and AUC) at the equivalent dose levels. After multiple oral doses for 15 days, the accumulation ratio was around 1-2. Partial responses were observed in all dose levels tested, including 2.5 mg BID, 5 mg BID and 5 mg QD.

In HMPL-689 4-week toxicity studies, the NOAEL were 0.5 mg/kg/day in dogs and 3 mg/kg/day in male rats, respectively. The AUC_{0-24h} was 754 h•ng/mL in male and 550 h•ng/mL in female for dogs, 1430 h•ng/mL in male rats for corresponded NOAELs, respectively.

According to total exposure of HMPL-689 in human and in preclinical toxicity studies, and the different protein binding rates of HMPL-689 in rat, dog and human, which was around 89.1%, 88.5% and 93.1%, respectively, the human equivalent dose of NOAEL, estimated by free exposure of HMPL-689, is likely to be 20-50 mg/day.

Based on the data above, HMPL-689 5 mg QD was selected as the initial dose in this study. A treatment cycle is defined as 28 days of continuous dosing.

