Intra-patient dose escalation to a higher dose level may be permitted by the sponsor provided that the dose level to be escalated has already been cleared at the time of dose increase being proposed.

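### Intra-patient escalation: Section 4.1.1.1 as worded imposes an unexplained gap of 27–28 missed daily doses, and Section 5.4.2 gives a different, looser rule for the same step

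*Protocol*

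**What the plan says.** Two places in the protocol set conditions for raising an individual patient's dose.

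- **Section 4.1.1.1** (under Stage 1) requires sponsor permission, and both the current and the higher level must be cleared of DLT. It then adds the interval: "There must be at least 28 days in-between the last dose of the current/lower dose level and the start of next/higher dose level". It also requires that "the patient must have tolerated the current/lower dose level". Section 4.1.1.5 sends the reader to 4.1.1.1 for patients who may benefit from a higher dose, and so carries the same rule.
- **Section 5.4.2** (after the DLT window of Stage 1, or in Stage 2) closes with a sentence that begins: "Intra-patient dose escalation to a higher dose level may be permitted by the sponsor provided that the dose level to be escalated has already". The remaining words only complete that condition: clearance of the higher level must precede the proposal. It states no other condition beyond sponsor permission and does not refer to 4.1.1.1.

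The background is continuous once-daily dosing. Section 4.2 states: "A treatment cycle is defined as 28 days of continuous dosing". Sections 4.1.1.5 and 5.2.4 do not allow missed doses to be made up.

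**The concern.** The interval in 4.1.1.1 runs from the last dose at one level to the first dose at the next, so it is a period without drug. It applies to someone with relapsed or refractory lymphoma who is tolerating treatment and for whom more benefit is sought. Followed literally, that patient goes untreated for about four weeks before the higher dose starts, for no stated reason.

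Section 5.4.2 errs the other way. A site using it alone would impose no interval, and would not see that this patient must have tolerated the current dose or that the current level must itself be cleared. Two sites could handle the same step differently, each pointing to protocol text.

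**Working it through.** **Inputs**

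- Minimum interval: 28 days, last lower dose to first higher dose (Protocol 4.1.1.1).
- Dosing: once daily at all planned levels (Protocol Table 2, Section 5.2.4).
- Half-life: geometric means across single-dose levels in healthy volunteers, "with values ranging from 7.06 to 9.37 hours" (Protocol 2.3).
- Exposure definitions: SAP 15. Dose group: initial dose received (SAP 6.2).

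**1. Missed doses.** Missed doses = (day of first higher dose − day of last lower dose) − 1.

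- 28 days elapsed (day 0 to day 28): 28 − 1 = 27.
- 28 full days in between (day 0 to day 29): 29 − 1 = 28.

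The rule is a minimum, so at least 27–28 doses are missed. If the 28 days meant time on the lower dose, the number would be 0.

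**2. Is it a drug washout?** Five half-lives are 5 × 7.06 = 35.3 h to 5 × 9.37 = 46.9 h, under two days. The gap is 28 × 24 = 672 h, which is 672 / 9.37 ≈ 72 to 672 / 7.06 ≈ 95 half-lives. Elimination of the drug does not explain it.

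**3. The two sections side by side**

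| Condition | 4.1.1.1 | 5.4.2 closing sentence |
|---|---|---|
| Sponsor permission | yes | yes |
| Higher level cleared | yes | yes |
| Current level cleared | yes | absent |
| 28-day interval | yes | absent |
| This patient tolerated the current dose | yes | absent |
| Cross-reference to the other section | no | no |

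**4. Effect on exposure estimates.** SAP 15 defines dose intensity as cumulative dose / total duration of exposure. Total duration runs from first to last dose, zero-dose days included. Relative dose intensity = dose intensity / initial assigned dose intensity × 100.

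Assumed case: 28 days at 5 mg, then 28 days at 10 mg. Cumulative dose = 28 × 5 + 28 × 10 = 420 mg.

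| Missed doses | Total duration (days) | Dose intensity (mg/day) | Relative dose intensity |
|---|---|---|---|
| 0 | 56 | 420 / 56 = 7.50 | 150% |
| 27 | 56 + 27 = 83 | 420 / 83 = 5.06 | 101% |
| 28 | 56 + 28 = 84 | 420 / 84 = 5.00 | 100% |

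With the gap, this patient moves from the SAP's top category (110% or more) to the 90% to <110% category.

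**The case against.** **The sponsor may have meant a real interval.** Section 4.1.1.5 concerns patients who have completed the 28-day DLT window, and cohorts run in sequence. A patient still on drug when the next level clears will therefore usually have had more than 28 days of dosing, and a rule asking for 28 days on dose would add little at a first escalation. It would matter mainly for patients added later to a level, or for a second escalation. A reader might infer that the 4.1.1.1 sentence is a proven slip for 28 days on treatment. The match with the cycle length and the DLT window makes that plausible, and 4.1.1.1 itself describes the patient as being on the current level, but no text says so. This part of the objection stands: the intent is an inference.

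**A short half-life rules out only a drug washout.** An observation period for late toxicity is another possible reason. The protocol follows safety for 30 days after the last dose (4.1.6) and uses 28-day resolution limits for several toxicities (6.8). Neither is tied to escalation anywhere, so this remains a possibility and not a stated reason. The accumulation ratio of about 1–2 in Section 4.2 comes from data that Section 2.3 calls unvalidated, across BID and QD dosing, so nothing here rests on it.

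**Section 5.4.2 does not cancel 4.1.1.1, and tolerability is partly covered elsewhere.** Sponsor permission is still needed. Section 5.4.2 also requires withholding or reduction for toxicity, and 5.8.4 requires stopping for intolerable toxicity. Stage 2 patients start at the RP2D, so escalation there would need a cleared level above it. All this limits the harm, but the sentence still sets out fewer conditions for the same act.

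**Conflict with the limit on interruptions.** A reader might see a direct conflict with the rule in 5.4.2 to discontinue after more than 14 consecutive days off drug. That rule concerns interruption due to toxicity only, so there is none.

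**Conclusion.** The point holds as a minor one. As worded, 4.1.1.1 costs a tolerating patient at least 27–28 daily doses with no reason in either document, and 5.4.2 governs the same step without three of the conditions in 4.1.1.1. The dose count assumes once-daily dosing up to the last lower dose. The statement about washout assumes that single-dose half-lives in healthy volunteers are a fair guide.

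A reader might infer from SAP 6.2 that no planned estimate is touched. That is not so: initial dose fixes the group, but the exposure summaries in SAP 15 do shift. The drop from 150% to 100–101% is for one assumed schedule and is not a forecast. The opposite inference, that the MTD is affected, is not supported either: DLTs are counted in Cycle 1, and "DLTs will be assessed during a DLT assessment window of 28 days".

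Practical reach is small. Escalation is optional and sponsor-approved, enrollment is halted (Amendment Summary), and the documents do not show whether any eligible patient remains on treatment or was ever subjected to the gap.

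**What to change.** First, the sponsor should confirm what was intended. If no dose-free interval was meant:

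- Replace the interval sentence in 4.1.1.1 with: *The patient must have completed at least 28 days of dosing at the current/lower dose level and tolerated it before starting the next/higher dose level.*
- Replace the closing sentence of 5.4.2 with: *Intra-patient dose escalation is permitted only under the conditions in Section 4.1.1.1.*

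If a dose-free interval was meant, give its reason in 4.1.1.1 and apply it in both sections through the same cross-reference.

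The cost is two sentences, in a clarification letter or the next amendment. No new procedures, data or analyses are needed.

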4.1.1.2 Definition of Dose Limiting Toxicity

Dose limiting toxicities are defined as the occurrence in the DLT assessment window of any of the following TEAEs, unless equivocally due to underlying malignancy or an extraneous cause:

- a. Non-hematologic toxicity: All non-hematologic TEAEs of Grade 3 or greater with the exception of:
 - i. Grade 3 nausea or vomiting that can be controlled by supportive therapy
- b. Hematologic toxicity:
 - i. Grade 4 neutropenia lasting for more than 5 days
 - ii. Grade 4 thrombocytopenia or Grade 3 thrombocytopenia with bleeding event or requiring platelet transfusion
 - iii. Grade ≥ 3 febrile neutropenia (defined as ANC $< 1000/\text{mm}^3$ with a single temperature $> 38.3^\circ\text{C}$ [101°F] or a sustained temperature of $\geq 38^\circ\text{C}$ [100.4°F] for more than 1 hour)
 - iv. Grade 4 anemia not explained by underlying disease
- c. Any TEAE requiring a dose delay of ≥ 15 days
- d. Any case of Hy's Law

4.1.1.3 Dose Limiting Toxicity Assessment Window

For all patients in Stage 1, DLTs will be assessed during a DLT assessment window of 28 days (i.e., from Cycle 1, Day 1 [the day of first administration of treatment] through Cycle 1, Day 28).

4.1.1.4 Definition of a DLT-Evaluable Patient

For decisions on dose escalation, each dose cohort shall present protocol-required number of DLT-evaluable patients. Any patient is DLT evaluable if he/she meets the following criteria:

A patient is DLT evaluable if he/she:

- has received at least 75% of the assigned dose of study treatment during the DLT assessment window (i.e., Days 1-28);
- or
- has not completed the DLT assessment period due to a DLT.

Patients who are not DLT evaluable in a dose cohort will be replaced to guarantee the protocol-required number of DLT-evaluable patients for each dose cohort.

4.1.1.5 Dosing Beyond Cycle 1

Patients who complete DLT assessment window and are deemed by the investigator to be benefiting from HMPL-689 treatment may continue with HMPL-689 treatment until disease progression, death, intolerable toxicity, at investigator's discretion that the patient can no longer benefit from the study treatment, withdrawal of consent, or the end of study, whichever occurs first. Conversely, if, in the opinion of the attending principal investigator, the patient may receive clinical benefit from a higher dose, then, at the request of the principal investigator and with the approval of the sponsor, the patient may be able to participate in intra-patient dose escalation (Section 4.1.1.1).

During the study treatment period, including the DLT assessment window, patients will not be allowed to make up missed doses.

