7 STATISTICAL ANALYSIS

7.1 Determination of Sample Size

CCI [REDACTED]. In general, the maximum sample size in the dose-escalation stage will be determined by sponsor and investigator based on the accumulated safety data and the mTPI-2 design (Ji 2013). CCI [REDACTED].

Patients who withdraw from the study prior to completing the DLT assessment window for reasons other than DLT or receive less than 75% of assigned study medication during DLT assessment window will be replaced. This may result in the actual enrollment exceeding the planned enrollment.

CCI [REDACTED]

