6.4. DLT EVALUABLE ANALYSIS SET (DEAS)

The DLT Evaluable Analysis Set (DEAS) is defined as all patients enrolled in the dose escalation phase of the study who are evaluable for DLT assessment. A subject is DLT evaluable if he/she meets the following criteria:

 has received at least 75% of the assigned dose of study medication during the DLT assessment window

OR

has not completed the DLT assessment period due to a DLT

DLT assessment window is defined as the treatment period of 28 days (i.e., from Cycle 1, Day 1 [the day of the first administration of treatment] through Cycle 1, Day 28).

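### A patient with at least 75% of doses who withdraws before Day 28 without a DLT is DLT-evaluable under one set of sections and must be replaced under another, and nothing says whether that patient stays in the DLT count

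*Protocol*

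**What the plan says.** **Evaluability.** Protocol 4.1.1.4 gives two alternative routes. The patient "has received at least 75% of the assigned dose of study treatment during the DLT assessment window", or the patient "has not completed the DLT assessment period due to a DLT". It then states: "Patients who are not DLT evaluable in a dose cohort will be replaced". The synopsis definition and Protocol 7.2 use the same two routes. SAP 6.4 says the DEAS "is defined as all patients enrolled in the dose escalation phase of the study who are evaluable for DLT assessment" and repeats them. None of these places asks a patient without a DLT to complete the window.

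**Replacement.** Protocol 7.1 has a different trigger. "Patients who withdraw from the study prior to completing the DLT assessment window for reasons other than DLT" are replaced, and so, as a separate alternative, are those who "receive less than 75% of assigned study medication during DLT assessment window will be replaced". The synopsis sample-size text and SAP 4.2 say the same. Early withdrawal is sufficient alone under this wording; the dose taken does not matter.

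**Window.** Protocol 4.1.1.3: "DLTs will be assessed during a DLT assessment window of 28 days". On missed doses, Protocol 4.1.1.5 adds that "patients will not be allowed to make up missed doses".

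**Use of the count.** Protocol 4.1.1.4 bases escalation decisions on DLT-evaluable patients. SAP 17.1 calculates DLT percentages on the DEAS. Incidence of DLTs is a primary endpoint of the escalation stage in Table 1 of both documents.

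**The concern.** The two definitions overlap. A patient who has taken 21 of 28 doses and then withdraws, without a DLT, before the window closes is evaluable under 4.1.1.4 and so not due for replacement there, yet must be replaced under 7.1. Neither document ranks the two rules. Replacement under 7.1 does not remove the patient from the DEAS either, because SAP 6.4 still admits anyone with 75% of the dose.

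Three counts are therefore open: keep the patient and do not replace; replace and drop; replace and keep. Under the first and third, someone not necessarily observed to Day 28 is scored as DLT-free in the denominator of a primary endpoint.

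The last days of the window do carry information. The DLTs reported in Protocol 2.3 from the earlier patient study were two asymptomatic Grade 3 amylase increases, which only testing can find. Protocol 5.7.10 schedules amylase and lipase on Days 8, 15 and 22 of Cycle 1 and then on Day 1 of Cycle 2. One DLT criterion, Grade 4 neutropenia lasting more than 5 days, depends on duration.

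**Working it through.** **1. Who is affected.** Doses are daily and the window is 28 days: 0.75 × 28 = 21 doses. Missed doses are not made up, so 21 doses cannot be reached before Day 21. The overlap covers non-DLT withdrawals from about Day 21 to Day 27, with at most 28 − 21 = 7 days unobserved.

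**2. Chance of a missed DLT.** Assume a constant hazard that continues after dosing stops. For a 28-day DLT rate p and exit after the dose on day d, the chance of a DLT in the remaining days, given none so far, is 1 − (1 − p)^((28 − d)/28).

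| Exit after | p = 20% | p = 30% | p = 35% |
|---|---|---|---|
| Day 21 | 5.4% | 8.5% | 10.2% |
| Day 22 | 4.7% | 7.4% | 8.8% |
| Day 27 | 0.8% | 1.3% | 1.5% |

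The Day 21 row is the maximum.

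**3. Reproducing Figure 1.** Inputs from Protocol 4.1.1: target 0.30, both epsilons 0.05. Assumptions, because the documents do not state them: a Beta(1,1) prior, and DU when P(p > 0.30 | data) > 0.95 with at least 3 patients. Taking the width-0.10 sub-interval with the largest unit probability mass reproduces all 90 cells.

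**4. Replaced and also retained.** One DLT-free patient is added to a full cohort, so x/n becomes x/(n + 1). Read from Figure 1:

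| Full cohort | Cells that change |
|---|---|
| 3 → 4 | none (0 E, 1 S, 2 D, 3 DU throughout) |
| 6 → 7 | 4/6 DU → 4/7 D |
| 9 → 10 | 5/9 DU → 5/10 D |

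The posterior explains both changes. P(p > 0.30) is 0.971 at 4/6 and 0.942 at 4/7; it is 0.953 at 5/9 and 0.922 at 5/10. Each pair straddles 0.95. The dose is still de-escalated, but the bar on its reuse is lifted. A move to escalation, 1/3 S → 1/5 E, needs two such patients at one dose level.

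**5. Counted instead of replaced.** In a cohort of 3 with one such patient and x DLTs in the two completers:

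| x | Counted | Replaced, replacement has no DLT | Replaced, replacement has a DLT |
|---|---|---|---|
| 0 | 0/3 E | 0/3 E | 1/3 S |
| 1 | 1/3 S | 1/3 S | 2/3 D |
| 2 | 2/3 D | 2/3 D | 3/3 DU |

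The decision differs only when the replacement has a DLT. With an assumed true rate of 30%, that has probability 0.30 (0.20 to 0.40 for rates of 20% to 40%). The probability of escalation is 0.7² = 0.49 if counted and 0.7³ = 0.343 if replaced. In a cohort of 6 at 30%, the decisions differ with probability 0.24, and escalation has probability 0.528 against 0.42.

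**The case against.** **The sections can be read together.** The second route in 4.1.1.4 excuses non-completion caused by a DLT, which suggests that other non-completion is not evaluable, as 7.1 in effect says. That is a sensible reading of intent. It is not what the text does: the 75% route stands alone, and SAP 6.4, from which the analysis set will be programmed, repeats it without the replacement rule.

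**Such patients may well be observed.** Protocol 5.8.4 separates stopping treatment from leaving the study. Section 6.2.5 collects all adverse events until 30 days after the last dose or new anti-neoplastic therapy, and 5.8.1 asks early leavers to return at 30 ± 7 days. This stands in large part, and limits the problem to patients not followed to Day 28. But follow-up is not a condition of evaluability, and withdrawal of consent or new therapy can end it early.

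**Enrolment is halted.** The Amendment 5 summary says so, so the remaining matter is mainly the DLT table and the counts behind the MTD. Section 5.8.4.1 also has the Safety Review Committee (SRC) review all data before escalation. Both points lower the stakes; neither fixes the denominator.

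**A stronger reading is tempting.** A reader might infer that the rule generally favours escalation. The documents do not support that. One retained patient in a full cohort never turns S into E or D into S. The 0.49 against 0.343 contrast compares a patient already known to be DLT-free up to withdrawal with a new patient at full risk, so the gap comes from that conditioning and does not measure bias in the rule.

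**Conclusion.** The contradiction is textual, does not depend on redacted content, and leaves the DEAS denominator undefined for this group. Followed literally, SAP 6.4 scores a replaced and possibly incompletely observed patient as DLT-free in a primary endpoint.

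The size is modest. The chance of a missed DLT is at most about 5% to 10% per such patient for 28-day rates of 20% to 35%, falling to about 1% for exit after Day 27 at a 30% rate. This rests on a constant hazard continuing after dosing stops. The effect of one replaced-and-retained patient on Figure 1 is confined to two DU-to-D cells at full cohorts of 3, 6 or 9. Neither document shows that any such patient existed, so it should not be inferred that the Stage 1 decisions or the MTD were affected. The change is still worth making, because the DLT rate could not be reproduced unambiguously if there was one.

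**What to change.** Reconcile both synopsis passages, Protocol 4.1.1.4, 7.1 and 7.2, and SAP 4.2 and 6.4 to one evaluability and replacement definition. With enrolment halted, the SAP text matters most:

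- In the DEAS, a patient without a DLT counts only if at least 75% of the assigned dose was taken and DLT status was ascertained through Day 28. A patient who did not complete the window because of a DLT continues to count.
- Patients replaced under 7.1 are left out of the DEAS and of the counts behind the DLT rate and the MTD.
- List any Stage 1 patient who took at least 75% of the dose and withdrew before Day 28 without a DLT, with the last day of DLT observation. If there are any, show the DLT rate with and without them, so that it can be matched to the counts the SRC used.

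The cost is a few sentences and one listing. The downside is that the DEAS may lose any such patient, and the reported rate could then differ from the one the SRC saw; the two-way display covers that. If there are none, the listing says so and nothing else changes.
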